1.6 Genomic characterization of HPV-associated and Tobacco-associated Oropharyngeal cancer

[figure not shown]
HPV- associated OPSCC has a different genomic profile as compared to HPV-negative, tobacco associated OPSCC³⁵. Seminal work done by Dr. [REDACTED] using the tumor cancer genome atlas has shown that HPV-negative tobacco associated OPSCC characteristically has p53 mutations and CCND1 amplifications. These genetic alterations are rarely (if ever) seen in HPV-associated OPSCC, especially those with minimal smoking histories. Dr [REDACTED] et al. have further characterized the tumor genomic profiles in patients with HPV- associated OPSCC with significant smoking histories ($>$ 10 pack years). They observed that not all HPV-associated OPSCC are the same on the genetic level, especially in those with $>$ 10 pack year smoking history [REDACTED] et al. used next-generation sequencing to analyze genetic mutations in 66 HPV-positive oropharyngeal cancer patients, who were also categorized into groups based on smoking history. They found that disease-free and overall survival were better in the less than 10-pack year group, and there were differences in mutations between the two groups based on smoking history. Mutations in genes such as TP53, CDKN2A, KRAS and NOTCH1 almost exclusively observed in the $>$ 10 pack-year group while HLA-A mutations were almost exclusively in the lighter smoking group. These data provide a molecular criteria based

on genomic mutations to help better stratify risk/prognosis and potentially to guide treatment selection, namely whether de-intensification should be used.

The proposed study aims to build upon the work of [REDACTED] et al. and [REDACTED] et al. by evaluating whether genomic profiling can be used to better select patients for de-intensification. By better selecting patients (using genomic profiling, see below) for de-intensification, we hypothesize that we can further improve the 2 year PFS to 93% for patients with HPV- associated OPSCC regardless of smoking history.

1.7 Circulating free HPV DNA (cfHPV-DNA)

Circulating cell free plasma DNA (cfDNA) can be a sensitive biomarker of tumor burden that is accessible by simple phlebotomy. Circulating free HPV DNA is detectable (via polymerase chain reaction) in patients with HPV-associated OPSCC and a highly specific circulating biomarker for HPV positive HNSCC. Limited data on a small number of patients have shown that cfHPV-DNA levels become largely undetectable post-CRT in most patients, and that cfHPV-DNA levels increase at the time of recurrence, thus suggesting that cfHPV-DNA may be prognostic³⁵⁻³⁷. UNC-LCCC has the unique ability to evaluate cfHPV-DNA using digital droplet PCR (ddPCR) technology. [name] lab has developed a ddPCR assay for HPV subtype 16 that is exquisitely sensitive and specific in laboratory tests, and has successfully detected cfHPV-DNA in 2 out of 2 patients that have been analyzed to date (Figure 1). In this study we will prospectively collect blood samples pre-treatment, during, and after treatment to evaluate the kinetics of cfHPV-DNA in all patients. We are particularly interested in the kinetics during treatment as it may be used to guide further studies: e.g. to help guide when to stop radiation or, if levels do not become undetectable during some point of treatment, one may change chemotherapy or continue with adjuvant chemotherapy.

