1.8 Rationale

The proposed study will build upon on our seminal prior phase II and genomic characterization studies by leveraging unique clinical/ translational strengths at UNC-LCCC: cancer genomics and cfHPV-DNA. Our over-arching hypothesis is that the

genomic characterization of OPSCC tumor specimens from patients with > 10 pack year smoking history can be used to help decide whether de-intensification would be efficacious.

Because of the positive results of our first two de-intensification studies (LCCC 1120, LCCC 1413) and the emerging genomic risk stratification data from [REDACTED] et al. and [REDACTED] et al., we are proposing conducting a similar study with the major modification of:

1. Tumor Genetics: Tumor genetics will be assessed in all patients with > 10 pack year smoking history, and select patients with extensive smokeless tobacco history, based on the PI's assessment. The UNC Molecular Genetics Laboratory will perform a mutation panel interrogating selected regions of 26 genes (p53 mutation is the most common to this patient population) using next-generation sequencing. P53 mutational status will be used to assess eligibility of patients with >10 pack years smoking history.
2. Circulating free HPV DNA: In this study we will prospectively collect blood samples pre-treatment, during, and after treatment to evaluate the kinetics of cfHPV-DNA in all patients.
3. Primary endpoint: Our hypothesis is that by using genomic profiling in the patients with HPV-associated OPSCC and > 10 pack year smoking history that we will be better able to select those patients with HPV-associated OPSCC who would safely benefit from de-intensification. The primary endpoint is PFS, however by using genomics to select the most favorable patients with a > 10 pack year smoking history, we estimate the PFS to be 93% (for the entire population, regardless of smoking), instead of the 87% as has been reported in previous studies¹⁰ and our prior studies.

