4.0 PATIENT ELIGIBILITY

4.1 Inclusion Criteria

- 4.1.1** ≥ 18 years of age (no upper age limit)
- 4.1.2** T0-3, N0 to N2c, M0 squamous cell carcinoma of the oropharynx (AJCC 7th edition)
- 4.1.3** Biopsy proven squamous cell carcinoma that is HPV and/or p16 positive
- 4.1.4** Radiologic confirmation of the absence of hematogenous metastasis within 12 weeks prior to treatment; at a minimum, chest x-ray is required. CT imaging of the chest or PET/CT is acceptable.
- 4.1.5** ECOG Performance Status 0-1
- 4.1.6** CBC/differential obtained within 8 weeks prior to treatment, with adequate bone marrow function defined as follows:
 - 4.1.6.1** Platelets $\geq 100,000$ cells/mm³
 - 4.1.6.2** Hemoglobin ≥ 8.0 g/dl (Note: The use of transfusion or other intervention to achieve Hgb ≥ 8.0 g/dl is acceptable.)
- 4.1.7** Adequate renal and hepatic function within 4 weeks prior to treatment, defined as follows:
 - 4.1.7.1** Serum creatinine < 2.0 mg/dl
 - 4.1.7.2** Total bilirubin $< 2 \times$ the institutional ULN

4.1.7.3 AST or ALT < 3 x the institutional ULN.

Note that physician attestation of patient having no known history of liver disease can take the place of bilirubin and AST/ALT labs.

- 4.1.8** Negative pregnancy test within 2 weeks prior to treatment for women of childbearing potential
- 4.1.9** Women of childbearing potential and male participants who are sexually active must practice adequate contraception during treatment and for 6 weeks following treatment.
- 4.1.10** Patients must be deemed able to comply with the treatment plan and follow-up schedule.
- 4.1.11** Patients must provide study specific informed consent prior to study entry

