5.3 HPV and/or p16 testing

HPV and/or p16 testing will be performed via fluorescence in-situ hybridization and immunohistochemistry, respectively. Methods and techniques for these tests have been established by the UNCH, UF, and Rex Cancer Center of Raleigh Departments of Pathology and these biomarkers are already routinely examined for all head and neck tumor specimens obtained at these institutions. This testing may be performed on FNA tissue obtained from a neck node. Results of HPV and/or P16 testing performed at institutions outside of the study site are acceptable.

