5.5 Circulating free HPV-DNA (cfHPV-DNA)

Previous versions of this protocol have detailed various requirements regarding blood specimen collection time points as the trial has evolved. These have included blood collection at pretreatment, weekly during treatment, and up to 5 post-treatment time points. As of May 8, 2020, blood specimens will only be collected at pre-treatment and Week 4 of treatment. One tube will be drawn at each time point. Circulating plasma DNA will be extracted and cfHPV-DNA will be quantified using our ddPCR assay using the Biorad QX-200 (████████ [name]'s lab). Additional exploratory analyses on plasma cfDNA samples may be performed in study co-investigator laboratories. Additional samples may be obtained at the PI's discretion. If necessary, each additional draw will be one Streck tube. UNC will provide Streck BCT tubes to other participating centers for blood collection. After sample is drawn, tube should be inverted 10 times to mix the preservative. Sites will overnight ship blood samples within one business day to UNC in FedEx boxes without ice for assessment (for samples collected on Friday, shipping on Monday is fine). If necessary for batch shipment, sites may wait to ship blood samples, but must ship within one week (5 business days) of the date the earliest sample was drawn.

Specimens will be retained indefinitely unless a specific participant chooses to withdraw from the study. Should a patient withdraw from this study, any specimens that have been collected, and that contain information that can be used to identify the participant will be destroyed. Any specimens that have been stripped of identifying information cannot be linked back to the participant, and therefore will not be destroyed.

Tissue and blood samples should be sent overnight (or by UNC courier) to ██████████ at the following address: Department of Radiation Oncology; UNC Cancer Hospital; [name]. Please notify ██████████ by phone ██████████ or email (██████████) when samples are shipped.

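### The only cfHPV-DNA assay described detects HPV16, yet eligibility covers any HPV and/or p16 positive tumour and section 7.2 defines no cfHPV-DNA evaluable set

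*Combined protocol and SAP*

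**What the plan says.** **Assay.** Section 1.7 reports that a UNC "lab has developed a ddPCR assay for HPV subtype 16", with clinical experience at that time of 2 out of 2 patients. Section 5.5, in the current text, says that "cfHPV-DNA will be quantified using our ddPCR assay using the Biorad QX-200". It names no HPV type and does not say that the assay was extended.

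**Population.** Section 4.1.3 requires "Biopsy proven squamous cell carcinoma that is HPV and/or p16 positive", so p16 positivity alone is enough. Section 5.3 says that "HPV and/or p16 testing will be performed via fluorescence in-situ hybridization and immunohistochemistry, respectively" and that "Results of HPV and/or P16 testing performed at institutions outside of the study site are acceptable". It describes no genotyping.

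**Use.** Section 1.8 (and 1.7 in almost the same words) plans blood sampling "to evaluate the kinetics of cfHPV-DNA in all patients". Section 2.2 hypothesises that changes in cfHPV-DNA correlate with cancer control. Section 3.2 lists copy-number kinetics as a secondary endpoint.

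**Analysis.** Section 7.2 compares levels before, during and after CRT by paired t-test or McNemar's test, and adds an exploratory joint model of longitudinal cfHPV-DNA and time to progression. It defines no evaluable set and gives no rule for an undetectable baseline.

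**The concern.** Set together, these sections admit patients whose marker the described assay cannot measure. They are patients with a non-16 HPV type and patients with a p16 positive tumour that carries no HPV DNA. The second group would stay invisible even to a multi-type assay. Both should read zero before treatment and at week 4 for a reason unrelated to response.

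The secondary hypothesis is that the marker tracks cancer control. A patient who reads zero by construction and then progresses counts as a failure at the lowest marker value. A patient who reads zero by construction and stays well adds no information about the marker. The estimated association then mixes biology with assay coverage. Section 1.7 hopes that on-treatment kinetics will inform the design of further studies, so the estimate should describe patients in whom the marker can move.

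**Working it through.** The documents give no sample size, power or effect size for the cfHPV-DNA analyses, so there is no stated figure to reproduce. The check takes each planned analysis in turn and then gives an illustration. Let f be the fraction of patients whose tumour the assay cannot see, and q their 2-year failure rate. Neither is in the documents.

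**Paired t-test.** If measurable patients have mean change m with SD s and invisible patients have change 0, the mean over everyone is (1−f)m and the variance is (1−f)s² + f(1−f)m². Assume a mean fall of 2 log10 units with SD 1, for a standardised change of 2.00.
- f = 10%: mean 0.9 × 2 = 1.8; variance 0.9 + 0.09 × 4 = 1.26; SD 1.122; standardised change 1.60.
- f = 20%: mean 1.6; variance 0.8 + 0.16 × 4 = 1.44; SD 1.20; standardised change 1.33.

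**McNemar's test.** The statistic uses only discordant pairs. An undetectable/undetectable patient is concordant, so including or excluding such patients leaves it unchanged.

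**Joint model.** This is the only planned analysis that links the marker to progression. Invisible patients contribute flat-zero trajectories with whatever event rate they have. No closed-form figure is available without a model specification, so the effect is shown through a simple grouping.

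**Grouping by on-treatment detectability (illustration, not a planned analysis).** Assumptions: measurable patients split equally into cleared (2% failure) and not cleared (12% failure), for a true risk ratio of 0.12/0.02 = 6.0. Invisible patients join the undetectable group.

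Observed risk in that group = [0.5(1−f) × 0.02 + f × q] / [0.5(1−f) + f]; observed risk ratio = 0.12 / that risk.

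For f = 10% and q = 12%: (0.009 + 0.012)/0.55 = 3.8%, so the ratio is 3.14.

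| f | q = 2% | q = 7% | q = 12% |
|---|---|---|---|
| 5% | 2.0%, ratio 6.0 | 2.5%, ratio 4.85 | 3.0%, ratio 4.06 |
| 10% | 2.0%, ratio 6.0 | 2.9%, ratio 4.12 | 3.8%, ratio 3.14 |
| 20% | 2.0%, ratio 6.0 | 3.7%, ratio 3.27 | 5.3%, ratio 2.25 |

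**A second set of assumptions, matched to the plan's 0.93 PFS.** Take 225 completers (section 7.1). Of the measurable patients, 30% are not cleared with 14% failure and 70% are cleared with 4% failure: 0.3 × 0.14 + 0.7 × 0.04 = 7% overall. The true ratio is 3.50, and power at two-sided 0.05 is 0.73 when f = 0.

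| f | q | ratio, all included | power, all included | power, invisible excluded |
|---|---|---|---|---|
| 10% | 7% | 3.17 | 0.67 | 0.69 |
| 20% | 7% | 2.92 | 0.61 | 0.65 |
| 10% | 14% | 2.61 | 0.57 | 0.69 |
| 20% | 14% | 2.11 | 0.41 | 0.65 |
| 20% | 4% | 3.50 | 0.69 | 0.65 |

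Exclusion restores the ratio to 3.50 throughout. It gains power when invisible patients do worse than cleared patients, and costs a little when they do equally well.

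**The case against.** Several stronger readings are tempting, and the documents do not support them.

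- **That invisible tumours cannot be told apart from cleared ones.** Section 5.5 keeps a pre-treatment sample. A cleared patient is detectable there and an invisible tumour is not, so zero-to-zero is no change rather than clearance. The gap is that 7.2 never says to use the baseline in this way.
- **That risk in the cleared group would be understated.** The arithmetic goes the other way. Adding patients who fail more often raises the observed risk, for example from 2% to 3.8%.
- **That 7.2 itself prescribes analysis of everyone.** It is silent. The all-patient wording is in sections 1.7 and 1.8, which are background and rationale. Counting these patients as undetectable is an inference from the missing rule.
- **That treatment in this trial is at risk.** No cfHPV-DNA result alters treatment here, and section 1.7 speaks of guiding further studies.

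The objector can add that 7.2 plans no clearance risk ratio and that every input to the illustration is assumed. With average-risk invisible patients, the second set of assumptions shows modest attenuation (3.50 to 3.17 at 10%) and a trivial power gain from exclusion. A baseline-detectable rule also removes HPV16 tumours that shed little DNA, so it mixes assay coverage with low shedding. All of this stands. It limits the size of the point and shapes the fix. It does not remove the mismatch between assay, population and analysis set.

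**Conclusion.** The point holds as a cheap improvement to secondary and exploratory analyses. The primary PFS test is untouched. The text describes an HPV16 assay, a population not restricted to HPV16, and no rule for patients without measurable marker.

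For the paired t-test, the effect is a smaller mean change. For the joint model, or any detectable/undetectable grouping, the usual effect is a weaker association with cancer control and an overstated failure risk among the apparently cleared. McNemar's statistic does not change.

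The size cannot be fixed from the documents. Under the first set of assumptions, the risk ratio of 6.0 falls to 4.1-4.9 at 5% invisible, 3.1-4.1 at 10% and 2.3-3.3 at 20%, if these patients fail at 7-12%. There is no attenuation if they fail at the cleared patients' rate. Section 1.4 reports worse survival in HPV-negative than in HPV-positive disease, which makes a higher failure rate plausible for p16-only tumours. That comparison was not made within p16 positive tumours, so it does not settle q.

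**What to change.** - **Section 5.5:** state which HPV types the assay in use covers, including any change during the trial.
- **Section 7.2:** define the cfHPV-DNA evaluable set for kinetics, clearance and association analyses as patients with detectable pre-treatment cfHPV-DNA on that assay.
- **Section 7.2:** report the number and PFS of baseline-undetectable patients separately. Note that this group mixes tumours the assay cannot see with low-shedding HPV16 tumours, and split it by tumour HPV type where that is already known.
- **Section 7.2:** give the all-patient analysis as a sensitivity analysis.

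The cost is wording only. The pre-treatment sample is already part of the schedule, so no new visit, sample or test is needed. The downside is a smaller analysis set, with a small loss of power if the excluded patients do as well as cleared patients.

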1.8 Rationale

The proposed study will build upon on our seminal prior phase II and genomic characterization studies by leveraging unique clinical/ translational strengths at UNC-LCCC: cancer genomics and cfHPV-DNA. Our over-arching hypothesis is that the

genomic characterization of OPSCC tumor specimens from patients with > 10 pack year smoking history can be used to help decide whether de-intensification would be efficacious.

Because of the positive results of our first two de-intensification studies (LCCC 1120, LCCC 1413) and the emerging genomic risk stratification data from [REDACTED] et al. and [REDACTED] et al., we are proposing conducting a similar study with the major modification of:

1. Tumor Genetics: Tumor genetics will be assessed in all patients with > 10 pack year smoking history, and select patients with extensive smokeless tobacco history, based on the PI's assessment. The UNC Molecular Genetics Laboratory will perform a mutation panel interrogating selected regions of 26 genes (p53 mutation is the most common to this patient population) using next-generation sequencing. P53 mutational status will be used to assess eligibility of patients with >10 pack years smoking history.
2. Circulating free HPV DNA: In this study we will prospectively collect blood samples pre-treatment, during, and after treatment to evaluate the kinetics of cfHPV-DNA in all patients.
3. Primary endpoint: Our hypothesis is that by using genomic profiling in the patients with HPV-associated OPSCC and > 10 pack year smoking history that we will be better able to select those patients with HPV-associated OPSCC who would safely benefit from de-intensification. The primary endpoint is PFS, however by using genomics to select the most favorable patients with a > 10 pack year smoking history, we estimate the PFS to be 93% (for the entire population, regardless of smoking), instead of the 87% as has been reported in previous studies¹⁰ and our prior studies.

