1.0 BACKGROUND AND RATIONALE

1.1 Study Synopsis

The proposed study is a follow-up study to LCCC 1120 and 1413. We have observed an excellent pathological complete response rate (LCCC 1120) and progression free survival (PFS) (LCCC 1413) in patients with HPV positive and/or p16 positive low-risk oropharyngeal squamous cell carcinoma (OPSCC) who received de-intensified chemoradiotherapy (CRT). We have shown that de-intensification is efficacious in these two phase II studies. We are leaders in the genomic classification of head and neck cancer, and investigators at LCCC ██████████ have shown that HPV-associated oropharyngeal cancer has a unique genetic profile. A major question is whether we can de-intensify in patients with HPV-associated oropharyngeal cancer who have smoking histories. The aim of the current study is to build upon our two phase II studies and the genomic profiling studies. Our hypothesis is that genomic profiling of patients' tumors (specifically for p53 mutations) will help in triaging patients to de-intensification versus standard of care. We will enroll patients with HPV-associated OPSCC regardless of smoking history and will assess p53 mutational status in patients with a smoking history. We will use the same de-intensification chemoradiotherapy regimen we have already evaluated in LCCC 1120 and 1413 in patients with HPV-associated OPSCC who have a minimal smoking history and in patients with a smoking history but with wild-type p53. If patients with a smoking history have mutated p53 they will not receive de-intensified chemoradiotherapy, but instead will receive standard doses. Our primary objective will be 2 year PFS. In LCCC 1413 the primary null hypothesis was 2 year PFS of 87%. We hypothesize, that by using genomics in the patients with a significant smoking history we will better select those who we can safely de-intensify and that the 2 year PFS will improve to 93%. We will also prospectively assess circulating free HPV DNA (cf-HPV-DNA) from blood samples. This study will be multi-institutional, with patients also enrolling at the University of Florida, Gainesville, Florida; the University of Florida Proton Therapy Institute, Jacksonville, FL; and Rex Cancer Center of Raleigh, Raleigh, North Carolina.

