2.0 STUDY OBJECTIVES

2.1 Primary Objective:

To evaluate whether genomic based risk-stratification can be used in deciding whether to de-intensify in patients with HPV-associated OPSCC with > 10 pack years smoking history. Hypothesis: Patients with HPV-associated OPSCC, > 10 pack years smoking history, and non-mutated p53 will have similar 2 year PFS as patients with < 10 pack years smoking history.

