3.0 ENDPOINTS

3.1 Primary Endpoint

Patients with HPV-positive and/or p16-positive OPSCC will receive de-intensified CRT. The 2 year PFS will be evaluated. Our null hypothesis (H_0) is that the PFS rate is 93% and our alternate hypothesis (H_1) is that the PFS rate is 86%.

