7.0 STATISTICAL CONSIDERATIONS

7.1 Study Design/Study Endpoints

The main objective of this Phase-II trial is to estimate the two-year progression-free survival probability (PFSP) in this group of patients treated with de-escalated radiotherapy. The planned total sample size is 80 patients. (This number was increased to 120 as of July 7, 2017, 140 as of February 7, 2019, 160 as of May 29, 2019, 180 as of October 9, 2019, 200 as of January 7, 2020, and 250 as of June 17, 2020. Please see details below.) The recruitment phase is expected to last 48 monthsDrop out is expected to be about 10%, based on a previous trial (LCCC 1120), hence we expect a total of 225 patients to complete the study.

The statistical aim is phrased as a hypothesis test with the null hypothesis being that the two-year PFSP is 0.93 and the alternative hypothesis being that the two-year PFSP is 0.86 (or less). A one sample binomial test will be used to assess this hypothesis. If the null hypothesis is rejected the conclusion will be that the de-escalated treatment is inferior to the standard treatment. If the null hypothesis is not rejected the conclusion will be that the de-escalated treatment is at least as good as the standard RT.

We give power calculations for two sample sizes. For a sample size of n=73 (patients who complete the study), the null hypothesis will be rejected if 11 or more patients fail. Failure is defined as not reaching the two-year time point progression-free. Defining P(Reject H0) to be the probability of rejecting the null hypothesis, the performance of the test is summarized in the following table.

True 2-year PFSP	P(Reject H0)
0.93	0.03
0.86	0.58
0.80	0.94
0.75	0.99

For a sample size of n=80 patients, the null hypothesis will be rejected if 12 or more patients fail. The performance of the test is summarized in the following table.

True 2-year PFSP	P(Reject H0)
0.93	0.02
0.86	0.57
0.80	0.94
0.75	0.99

For n=73 to 78, the critical point is 11 failures. For n=79 and 80, the critical point is 12 failures. With these critical points, type-I error ranges from 0.023 to 0.045 depending on sample size.

Sample size and power re-calculation: On July 7, 2017, the PI, noticing the higher than expected patient accrual rate, decided to increase sample size to 120. This should result in

about 108 patients to complete the study, after accounting for drop-out with an expected drop-out rate of 10%.

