0.75	1.00

For n=159 to 161, the critical point is also 18 failures. With these critical points, type-I error ranges from 0.030 to 0.035 depending on sample size.

Sample size and power re-calculation: On January 7, 2020, the PI, waiting for the opening of LCCC 1912 and noticing the completion of accruing planned 180 patients, decided to increase sample size to 200. This should result in about 180 patients to complete the study, after accounting for drop-out with an expected drop-out rate of 10%.

For a sample size of n=180 patients, the null hypothesis will be rejected if 19 or more patients fail. The performance of the test is summarized in the following table.

True 2-year PFSP	P(Reject H0)
0.93	0.048
0.86	0.93
0.80	0.99
0.75	1.00

For n=177 to 179, the critical point is also 19 failures. With these critical points, type-I error ranges from 0.042 to 0.048 depending on sample size.

Sample size and power re-calculation: On June 17, 2020, the PI, waiting for the opening of LCCC 1912 and noticing the completion of accruing planned 200 patients, decided to increase sample size to 250. This should result in about 225 patients to complete the study, after accounting for drop-out with an expected drop-out rate of 10%.

For a sample size of n=225 patients, the null hypothesis will be rejected if 23 or more patients fail. The performance of the test is summarized in the following table.

True 2-year PFSP	P(Reject H0)
0.93	0.045
0.86	0.96
0.80	0.99
0.75	1.00

For n=220 to 224, the critical point is also 23 failures. With these critical points, type-I error ranges from 0.036 to 0.045 depending on sample size.

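### The 93% null is an unsupported whole-cohort hope credited to p53 selection, and the pooled test against it cannot show whether selection works

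*Combined protocol and SAP*

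**What the plan says.** Section 1.8 (Rationale) attributes the reference rate to genomic selection among patients with more than 10 pack years: "we estimate the PFS to be 93% (for the entire population, regardless of smoking), instead of the 87% as has been reported in previous studies". It sources the 87% to reference 10 and to the sponsor's own prior studies. Sections 1.1 and 1.6 repeat the 93% expectation, and Section 1.1 also gives 87% as the null hypothesis of LCCC 1413.

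Selection reaches only part of the cohort. By Sections 5.1 and 5.4, p53 is tested in patients with more than 10 pack years and in select patients with extensive smokeless tobacco use. Everyone with 10 pack years or fewer is de-intensified, with the regimen already used in LCCC 1120 and 1413 (Section 1.1).

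Section 2.1 defines success differently, as a comparison between groups: patients with more than 10 pack years and "non-mutated p53 will have similar 2 year PFS as patients with < 10 pack years smoking history".

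The test is pooled. Section 7.1 has "the null hypothesis being that the two-year PFSP is 0.93", with 0.86 or less as the alternative. "A one sample binomial test will be used to assess this hypothesis". "Failure is defined as not reaching the two-year time point progression-free". The current rule is: "For a sample size of n=225 patients, the null hypothesis will be rejected if 23 or more patients fail". Rejection is to be read as inferiority of the de-escalated treatment to the standard one. Section 7.2 adds a log-rank comparison of the two smoking groups (the heavier one without p53 mutation) and a Kaplan-Meier curve for PFS.

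**The concern.** A null rate normally describes what the comparator achieves. Here it is the rate the investigators hope for, six points above the rate they cite from earlier work. The whole rise is credited to a selection step that leaves patients with 10 pack years or fewer exactly as before. No smoker share, PFS by smoking group or calculation links 87% to 93%.

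Two things are at stake. First, a cohort that merely matches the cited benchmark would be reported as inferior to standard treatment. Second, the primary objective is whether p53 status can guide de-intensification, but the decision rule counts failures from all patients together. A poor result in lighter smokers would count against a strategy that never touched them, and a good one would be credited to it.

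**Working it through.** **Inputs.** From the documents: null 0.93 and alternative 0.86 (Sections 3.1, 7.1); n = 225, reject at 23 or more failures (Section 7.1); benchmark 0.87 (Sections 1.1, 1.8). Not in the documents: the share f of patients with more than 10 pack years, and 2-year PFS by smoking group. Both are assumptions below, shown over a range.

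**Step 1: reproduce the plan's figures.** P(reject) = P(X ≥ 23), with X binomial(225, 1 − PFS).
- PFS 0.93: 0.0446 (printed 0.045).
- PFS 0.86: 0.963 (printed 0.96).

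**Step 2: the same rule at the benchmark.** PFS 0.87 gives P(reject) = 0.913. At n = 220 with the same cut-off it is 0.892. The printed table covers 0.93, 0.86, 0.80 and 0.75, so this value is not shown. Rejection reaches 50% at a cohort PFS of about 0.899.

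**Step 3: reading A, 87% is the rate in patients with 10 pack years or fewer.** For the cohort to reach 0.93, heavier smokers would need p with f·p + (1 − f)·0.87 = 0.93, so p = 0.87 + 0.06/f. That is 1.17, 1.07, 1.02 and 0.99 at f = 20%, 30%, 40% and 50%; it exceeds 1 for f below 0.06/0.13 = 46%.

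If heavier smokers instead reach 0.93, the failures are the sum of two binomials (failure rates 0.13 and 0.07):

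| Share f | Cohort PFS | P(reject) |
|---|---|---|
| 20% | 0.882 | 0.80 |
| 30% | 0.888 | 0.71 |
| 40% | 0.894 | 0.61 |
| 50% | 0.900 | 0.49 |

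If both groups are at 0.87, Section 2.1 is met and P(reject) is the 0.913 of Step 2.

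**Step 4: reading B, 87% is an average over all smokers before selection.** Suppose a working strategy brings heavier smokers level with lighter ones. If lighter smokers are already at 0.93, unselected heavier smokers must have been at 0.93 − 0.06/f: 0.63, 0.73, 0.78 and 0.81 at f = 20%, 30%, 40% and 50%. The cohort then reaches 0.93 and P(reject) = 0.045.

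Intermediate cases at f = 30%, with unselected heavier smokers at b, put lighter smokers at (0.87 − 0.3b)/0.7:

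| b | Lighter smokers, and cohort if strategy works | P(reject) |
|---|---|---|
| 0.75 | 0.921 | 0.12 |
| 0.80 | 0.900 | 0.49 |
| 0.85 | 0.879 | 0.84 |

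**Step 5: what the pooled count can show.** Under the rule, a cohort PFS of 0.90 gives P(reject) = 0.49 whether it comes from both groups at 0.90 (similar, as Section 2.1 hopes) or from lighter smokers at 0.87 and heavier smokers at 0.93 in equal shares. The failure count does not distinguish these.

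**The case against.** The strongest reply is that the 87% need not describe lighter smokers. Section 1.8 cites reference 10, the analysis of the randomised trial in Section 1.4, in which pack-years was a stratifying factor. The wording sets a rate for the entire population against 87%, which can be read as one all-comer average against another. Section 1.6 reports better disease-free survival in lighter smokers. On that reading Sections 1.8 and 2.1 agree, and a working strategy may be rejected only 4.5% of the time.

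This stands. A reader might infer from Step 3 that a working strategy would usually be declared inferior, that 93% is arithmetically impossible, or that Section 1.8 contradicts Section 2.1. The documents support none of these as a plain finding, because each needs 87% to be the rate at 10 pack years or fewer and no section says so. Eligibility for LCCC 1120 (10 pack years or fewer) leans that way. But LCCC 1413 also took remote smokers up to 30 pack years, its 87% was a null hypothesis, and Section 1.5 gives it a median follow-up of only 6.9 months.

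The reply does not supply the missing justification. Reading B needs large gaps between smoking groups that the plan never states, and Section 1.4 also cites a study in which more than 10 pack years did not affect recurrence-free survival.

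Two further replies are partly right. Near-certain rejection at 0.87 is unsurprising when 0.96 is printed at 0.86; but 0.87 is the plan's own benchmark, and the reader should see how the rule treats it. Section 7.2 does compare smoking groups; but its log-rank test gives no group 2-year estimate, does not enter the primary conclusion, and cannot show similarity by being non-significant.

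**Conclusion.** The concern holds in this form. The 93% null is a hoped-for whole-cohort rate with no derivation, and the pooled verdict cannot answer the question in Section 2.1. Under the current rule, a cohort at 87% is called inferior to standard treatment with probability 0.91. That figure needs no assumption about smoking groups.

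The inferiority wording is not earned. By Section 1.8 the 87% comes partly from reference 10, which Section 1.4 describes as standard-intensity treatment. Section 6.2 describes the same trial as using the de-intensified treatment, and those two passages should be reconciled.

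The chance of rejecting a working strategy is undetermined: 0.80 to 0.49 for shares of 20% to 50% if 87% belongs to lighter smokers and heavier smokers reach 93%, and as low as 0.045 if 87% is an all-smoker average. The range reflects inputs the plan should have given.

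**What to change.** 1. **Section 7.1.** Add a 0.87 row, P(reject) = 0.91, to the n = 225 table. State that rejection means PFS below the hypothesised 93%, not inferiority to standard treatment.
2. **Section 7.2.** Report 2-year PFS with 95% CI separately for patients with 10 pack years or fewer, patients with more than 10 pack years and wild-type p53, and patients with more than 10 pack years and mutated p53. The last group is kept apart because it is not de-intensified. Report the difference in 2-year PFS with 95% CI between the first two groups. Base any conclusion on genomic selection on that difference, not on the pooled test or a non-significant log-rank.
3. **Sections 1.1, 1.6 and 1.8.** Present 93% as an assumption, not as a consequence of genomic selection.

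**Cost.** Wording, one table row and a few estimates from data already being collected; enrolment and treatment do not change. The genomics conclusion will rest on fewer patients. At about 90% PFS the half-width is 1.96·√(0.09/n): 8.8 points for 45 patients and 5.6 for 112 (20% and 50% of 225). For the difference it is wider: 1.96·√(0.09/45 + 0.09/180) = 9.8 points at 45 against 180, and 7.8 at 112 against 113. Taking p53-mutated patients out of the heavier-smoking group widens it further. That imprecision is present in the trial now; the pooled test only hides it.
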